## 6 STUDY INTERVENTION DISCONTINUATION AND PARTICIPANT DISCONTINUATION/WITHDRAWAL

### 6.1 DISCONTINUATION OF STUDY INTERVENTION

Discontinuation from the study intervention (PICO vs xeroform dressing) does not mean discontinuation from the study, and remaining study procedures should be completed as indicated by the study protocol. If a clinically significant finding is identified (including, but not limited to changes from baseline) after enrollment, the investigator or qualified designee will determine if any change in participant management is needed. Any new clinically relevant finding will be reported as an adverse event (AE).

The data to be collected at the time of study intervention discontinuation will include the following:

- Wound photograph
- Assessment of adverse events
- Assessment of concomitant medications

### 6.2 PARTICIPANT DISCONTINUATION/WITHDRAWAL FROM THE STUDY

Participants are free to withdraw from participation in the study at any time upon request.

An investigator may discontinue or withdraw a participant from the study for the following reasons:

- Significant study intervention non-compliance
- If any clinical adverse event (AE), laboratory abnormality, or other medical condition or situation occurs such that continued participation in the study would not be in the best interest of the participant

Subjects who sign the informed consent form and are randomized but do not receive the study intervention may be replaced. Subjects who sign the informed consent form, and are randomized and receive the study intervention, and subsequently withdraw, or are withdrawn or discontinued from the study will not be replaced.

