### 5.3 STUDY INTERVENTION COMPLIANCE

*Define how adherence to the protocol (e.g., administration of study intervention, use of device,) will be assessed, and verified (if applicable, e.g., plasma assays, electronic monitoring devices, daily diaries). Include a discussion of what documents are mandatory to complete (e.g., participant drug log) and what source documents/records will be used to calculate study intervention compliance.*

For both the Treatment Group and the Control Group, the dressings will remain in place until post-op day (POD) #5. Following dressing removal on POD #5, participants in both groups will be given identical wound management instructions. Photographs of each participant's healing wound will be obtained on POD #5 (+1 day) and on their first post-op clinic visit, approximately POD #14-21, and at POD #30 (+7 days). Participants who do not come to their designated follow-up appointments will be dropped from the dataset.

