### 6.3 LOST TO FOLLOW-UP

A participant will be considered lost to follow-up if he or she fails to return for 2 scheduled visits and is unable to be contacted by the study site staff.

The following actions must be taken if a participant fails to return to the clinic for a required study visit:

- The site will attempt to contact the participant and reschedule the missed visit and counsel the participant on the importance of maintaining the assigned visit schedule and ascertain if the participant wishes to and/or should continue in the study.
- Before a participant is deemed lost to follow-up, the investigator or designee will make every effort to regain contact with the participant (where possible, 3 telephone calls and, if necessary, a certified letter to the participant's last known mailing address or local equivalent methods). These contact attempts should be documented in the participant's medical record or study file.
- Should the participant continue to be unreachable, he or she will be considered to have withdrawn from the study with a primary reason of lost to follow-up.

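### Section 6.2 allows withdrawal from the study for undefined non-compliance, in tension with 6.1; together with 5.3 this can remove Day 30 outcomes after randomisation

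*Combined protocol and SAP*

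**What the plan says.** Four sections of the combined protocol and SAP bear on who stays in the comparison.

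- **Section 6.2** opens its list with "An investigator may discontinue or withdraw a participant from the study for the following reasons". The first reason is "Significant study intervention non-compliance"; the second concerns the participant's safety and best interest. No threshold or adjudication is given for the first. Treated participants who "subsequently withdraw, or are withdrawn or discontinued from the study will not be replaced".
- **Section 6.1** says that discontinuing the dressing "does not mean discontinuation from the study, and remaining study procedures should be completed as indicated by the study protocol". It then has a list headed "The data to be collected at the time of study intervention discontinuation will include the following": a wound photograph, adverse events and concomitant medications.
- **Section 5.3**, where compliance should be defined, still carries the unfilled template prompt. Its only adherence standard, for both arms, is that "the dressings will remain in place until post-op day (POD) #5". It adds: "Participants who do not come to their designated follow-up appointments will be dropped from the dataset".
- **Section 6.3** counts a participant as lost only if he or she "fails to return for 2 scheduled visits" and cannot be contacted. It tells the site to try to rebook a missed visit.

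Section 8 gives the endpoint and a sample-size paragraph. It names no analysis population, no intention-to-treat rule and no method for missing data. Only the photograph raters are described as blinded.

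**The concern.** Randomisation protects the comparison only if participants stay in it for reasons unrelated to their treatment or its result. Withdrawal for non-compliance with the assigned dressing is tied to treatment by definition, and may be tied to healing as well. Percentage graft take is read at Day 30, so a participant whose follow-up ends earlier may contribute no outcome.

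The two dressings look different and blinding is described only for the raters, so whoever makes the 6.2 decision probably knows the arm. An undefined, discretionary criterion applied with that knowledge could remove different kinds of participant from each arm. Section 8.2 says the pilot is meant to show whether a larger trial is worth pursuing, and a distorted arm difference would feed straight into that decision.

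**Working it through.** **The plan's own figure.** The only statistical figure is 44 per group (Section 8.2: 80% graft take, 80% power). It cannot be reproduced from the stated inputs, because no comparator value, standard deviation, alpha or sidedness is given. For example, 80% against about 52%, two-sided 0.05 without continuity correction, gives 44, and so does a standardised difference of 0.60. This point does not depend on that figure.

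**Two cases under the text.**

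1. *The dressing comes off before POD 5 and the participant is willing to attend.* Under 6.1 a photograph is taken at that time and the POD 14 and POD 30 photographs follow. Under 6.2 the investigator may instead treat the event as non-compliance and end study participation, after which no further study photograph is due. The plan does not say which section governs.
2. *The participant misses the POD 14 visit but attends POD 30.* Under 6.3 the visit is rebooked and the participant is not lost. Under a literal reading of 5.3 the participant leaves the dataset although a Day 30 photograph exists.

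**Size.** Inputs: 20 participants (Section 8.2) randomised 1:1 (Section 5.2), so about 10 per arm. Let k be the number removed from an arm, R the mean take of those retained and X the mean take of those removed.

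- Mean of all randomised = [(10 − k) × R + k × X] / 10
- Shift from removal = R − that mean = (k / 10) × (R − X)

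The documents give neither k nor the gap R − X. With assumed values:

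| Removed (k) | Gap 10 points | Gap 40 points |
|---|---|---|
| 1 | 1 | 4 |
| 2 | 2 | 8 |
| 3 | 3 | 12 |

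Worked example: k = 1, R = 90, X = 50. The mean of all ten is (9 × 90 + 50) / 10 = 86, against 90 after removal, a shift of 4 points.

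Cross-check from the other direction: suppose an arm truly averages 80% and one participant with 60%, 40% or 0% take is removed. The retained means are (800 − 60) / 9 = 82.2, (800 − 40) / 9 = 84.4 and 800 / 9 = 88.9, shifts of 2.2, 4.4 and 8.9 points.

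The arm difference moves by the shift in one arm minus the shift in the other. Equal removals with equal gaps cancel; unequal ones do not.

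**The case against.** Several stronger readings are tempting, and the documents do not support them.

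- *That 6.1 and 6.2 contradict each other.* Section 6.1 says stopping the dressing does not in itself end participation. Section 6.2 is a separate, permissive power, so both can be followed. They are in tension and need a linking rule.
- *That device failures are removed from the comparison.* Nothing equates a lost seal or a stopped pump with non-compliance. The plainer reading is that these are discontinuation of the intervention under 6.1, with follow-up continuing.
- *That 6.2 withdrawals are excluded from analysis.* The plan does not say so. The only explicit removal rule is in 5.3, and it concerns missed appointments.
- *That the bias favours NPWT.* Section 5.3 sets the same standard for both arms, and a gauze dressing can also come off early. That the investigator knows the arm is itself an inference, though a reasonable one.
- *That the device-failure rate is concealed.* Section 9.1.6 requires non-compliance to be reported as a protocol deviation, and Section 7.2.4 records adverse events regardless of relationship.

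It is also fair to say that 6.3 defines a status while 5.3 governs the dataset, that the 6.2 power may never be used, that the bar on replacing treated participants does not add to the bias, and that this is a pilot.

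These objections limit the claim but do not remove it. The 6.2 criterion is undefined, a withdrawn participant may have no Day 30 photograph, 5.3 and 6.3 treat a single missed visit differently, and nothing in Section 8 says who is analysed.

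**Conclusion.** The concern holds in a limited form. As written, the plan permits Day 30 outcomes to be lost or discarded after randomisation for reasons that may depend on treatment, through discretionary withdrawal in 6.2 and the attendance rule in 5.3. Removing only the 5.3 sentence would leave the 6.2 route open.

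Each removal is about 10% of an arm. One removal shifts that arm's mean by about 1 to 4 points over assumed gaps of 10 to 40 points, and more removals scale this in proportion. These are illustrations: the frequency, the gap and the direction are all unknown, and the possibility of a difference between arms rests on the inference that the investigator knows the allocation. Severity: should-fix, with moderate confidence.

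**What to change.** 1. In 6.2, remove intervention non-compliance as a reason for ending study follow-up. Leave the participant-safety reason unchanged. This concerns data collection only, not when a dressing should be stopped.
2. State in 6.1 and 6.2 that participants who stop or lose the dressing still have the scheduled POD 14 and POD 30 photographs, as 6.1 already intends.
3. Replace the removal sentence in 5.3 with an analysis-set rule, repeated in Section 8: all randomised participants with a Day 30 photograph are analysed in their assigned arm. Report missing photographs and withdrawals by arm and reason.
4. Align 5.3 with 6.3, so that one missed visit does not remove a participant who later supplies a Day 30 photograph.

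The cost is protocol wording, since the visits and photographs are already in the Schedule of Activities. The downside is that the estimate will include non-adherent participants and may look less favourable to either arm. Reporting device failures as a pilot outcome would be a useful option, but it needs a definition and a data item that the schedule does not now contain.

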### 6.3 LOST TO FOLLOW-UP

A participant will be considered lost to follow-up if he or she fails to return for 2 scheduled visits and is unable to be contacted by the study site staff.

The following actions must be taken if a participant fails to return to the clinic for a required study visit:

- The site will attempt to contact the participant and reschedule the missed visit and counsel the participant on the importance of maintaining the assigned visit schedule and ascertain if the participant wishes to and/or should continue in the study.
- Before a participant is deemed lost to follow-up, the investigator or designee will make every effort to regain contact with the participant (where possible, 3 telephone calls and, if necessary, a certified letter to the participant's last known mailing address or local equivalent methods). These contact attempts should be documented in the participant's medical record or study file.
- Should the participant continue to be unreachable, he or she will be considered to have withdrawn from the study with a primary reason of lost to follow-up.

## 7 STUDY ASSESSMENTS AND PROCEDURES

### 7.1 STUDY ASSESSMENTS

Subjects aged 18 or older who are undergoing surgery with reconstructive repair for a head and neck condition as part of routine clinical care will be approached to participate in the study. Subjects screened and enrolled will follow the schedule of events provided in Section 1.2. The following evaluations will be performed:

#### Screening (Day -7 to Day -1)

- Obtain written informed consent
- Obtain demographic information
- Obtain medical history
- Obtain concomitant medication information

#### Baseline/Day of Surgery (Day 0)

- Randomization into the Treatment Group or Control Group, as per measures outlined in Section 6.2
- Study device administration to subjects in both the Treatment Group and the Control Group
- Assessment of adverse events
- Assessment of concomitant medications

#### POD #5 (Day 5 +2)

- Photograph of wound healing
- Assessment of adverse events
- Assessment of concomitant medications

#### POD #14 (Day 14 +7)

- Photograph of wound healing
- Assessment of adverse events
- Assessment of concomitant medications

### POD #30 (Day 30 +7)

- Photograph of wound healing
- Assessment of adverse events
- Assessment of concomitant medications

The wound photographs will be de-identified, and a 10x10 grid digitally overlain on each image. The de-identified images will be randomized and given to two independent raters for assessment of wound healing.

## 7.2 ADVERSE EVENTS AND SERIOUS ADVERSE EVENTS

### 7.2.1 DEFINITION OF ADVERSE EVENTS (AE)

Adverse event means any untoward medical occurrence associated with the use of an intervention in humans, whether or not considered intervention-related (21 CFR 312.32 (a)).]

### 7.2.2 DEFINITION OF SERIOUS ADVERSE EVENTS (SAE)

An adverse event (AE) is considered “serious” if, in the view of either the investigator or sponsor, it results in any of the following outcomes:

- Death
- a life-threatening adverse event (of note, the term “life-threatening” refers to an event in which the subject was at risk of death at the time of the event, rather than to an event which hypothetically might have caused death if it were more severe)
- inpatient hospitalization or prolongation of existing hospitalization
- a persistent or significant incapacity or substantial disruption of the ability to conduct normal life functions
- or a congenital anomaly/birth defect.

Important medical events that may not result in death, be life-threatening, or require hospitalization may be considered serious when, based upon appropriate medical judgment, they may jeopardize the subject and may require medical or surgical intervention to prevent one of the outcomes listed in this definition. Examples of such medical events include allergic bronchospasm requiring intensive treatment in an emergency room or at home, blood dyscrasias or convulsions that do not result in inpatient hospitalization, or the development of drug dependency or drug abuse.

### 7.2.3 CLASSIFICATION OF AN ADVERSE EVENT

#### 7.2.3.1 SEVERITY OF EVENT

For adverse events (AEs) not included in the protocol defined grading system, the following guidelines will be used to describe severity.

- **Mild** – Events require minimal or no treatment and do not interfere with the participant’s daily activities.
- **Moderate** – Events result in a low level of inconvenience or concern with the therapeutic measures. Moderate events may cause some interference with functioning.

- **Severe** – Events interrupt a participant’s usual daily activity and may require systemic drug therapy or other treatment. Severe events are usually potentially life-threatening or incapacitating. Of note, the term “severe” does not necessarily equate to “serious”.

---

#### 7.2.3.2 RELATIONSHIP TO STUDY INTERVENTION

All adverse events (AEs) must have their relationship to study intervention assessed by the clinician who examines and evaluates the participant based on temporal relationship and his/her clinical judgment. The degree of certainty about causality will be graded using the categories below. In a clinical trial, the study product must always be suspect.

- **Related** – The AE is known to occur with the study intervention, there is a reasonable possibility that the study intervention caused the AE, or there is a temporal relationship between the study intervention and event. Reasonable possibility means that there is evidence to suggest a causal relationship between the study intervention and the AE.
- **Not Related** – There is not a reasonable possibility that the administration of the study intervention caused the event, there is no temporal relationship between the study intervention and event onset, or an alternate etiology has been established.

---

#### 7.2.3.3 EXPECTEDNESS

The Principal Investigator will be responsible for determining whether an adverse event (AE) is expected or unexpected. An AE will be considered unexpected if the nature, severity, or frequency of the event is not consistent with the risk information previously described for the study intervention.

---

#### 7.2.4 TIME PERIOD AND FREQUENCY FOR EVENT ASSESSMENT AND FOLLOW-UP

The occurrence of an adverse event (AE) or serious adverse event (SAE) may come to the attention of study personnel during study visits and interviews of a study participant presenting for medical care, or upon review by a study monitor.

All AEs including local and systemic reactions not meeting the criteria for SAEs will be captured on the appropriate case report form (CRF). Information to be collected includes event description, time of onset, clinician’s assessment of severity, relationship to study product (assessed only by those with the training and authority to make a diagnosis), and time of resolution/stabilization of the event. All AEs occurring while on study must be documented appropriately regardless of relationship. All AEs will be followed to adequate resolution.

Any medical condition that is present at the time that the participant is screened will be considered as baseline and not reported as an AE. However, if the study participant’s condition deteriorates at any time during the study, it will be recorded as an AE.

Changes in the severity of an AE will be documented to allow an assessment of the duration of the event at each level of severity to be performed. AEs characterized as intermittent require documentation of onset and duration of each episode.

The Study Coordinator will record all reportable events with start dates occurring any time after informed consent is obtained until 7 (for non-serious AEs) or 30 days (for SAEs) after the last day of study participation. At each study visit, the investigator will inquire about the occurrence of AE/SAEs since the last visit. Events will be followed for outcome information until resolution or stabilization.

### 7.2.5 ADVERSE EVENT AND SERIOUS ADVERSE EVENT REPORTING

All serious adverse events must be reported to the IRB according to regulatory requirements. The Principal Investigator will immediately report to the sponsor any serious adverse event, whether or not considered study intervention related, including those listed in the protocol or package insert and must include an assessment of whether there is a reasonable possibility that the study intervention caused the event. Study endpoints that are serious adverse events (e.g., all-cause mortality) must be reported in accordance with the protocol unless there is evidence suggesting a causal relationship between the study intervention and the event (e.g., death from anaphylaxis). In that case, the investigator must immediately report the event to the sponsor.

All serious adverse events (SAEs) will be followed until satisfactory resolution or until the Principal Investigator deems the event to be chronic or the subject is stable. Other supporting documentation of the event may be requested and should be provided as soon as possible.

## 8 STATISTICAL CONSIDERATIONS

### 8.1 STATISTICAL HYPOTHESES

Primary Endpoint(s): Progression of wound healing, as measured by comparison of photographs of all subject wounds taken at post-operative Day 5, post-operative Day 14-21, and post-operative Day 30. Percentage skin graft take will be evaluated on Day 30 by blinded, independent raters.

### 8.2 SAMPLE SIZE DETERMINATION

Our statistics indicate that assuming an 80% graft take, the number of patients needed for an appropriately powered study (80%) would be 44 patients in each group; however, we plan to only recruit 20 participants total, making this more of a pilot study to see if it's worthwhile to pursue a larger, prospective randomized controlled trial, given the costs associated with the devices to be used in this study.

## 9 SUPPORTING DOCUMENTATION AND OPERATIONAL CONSIDERATIONS

### 9.1 REGULATORY, ETHICAL, AND STUDY OVERSIGHT CONSIDERATIONS

#### 9.1.1 INFORMED CONSENT PROCESS

##### 9.1.1.1 CONSENT/ASSENT AND OTHER INFORMATIONAL DOCUMENTS PROVIDED TO PARTICIPANTS

Consent forms describing in detail the study intervention, study procedures, and risks are given to the participant and written documentation of informed consent is required prior to starting intervention/administering study intervention.

##### 9.1.1.2 CONSENT PROCEDURES AND DOCUMENTATION

Informed consent is a process that is initiated prior to the individual's agreeing to participate in the study and continues throughout the individual's study participation. Consent forms will be Institutional

Review Board (IRB)-approved and the participant will be asked to read and review the document. The investigator will explain the research study to the participant and answer any questions that may arise. A verbal explanation will be provided in terms suited to the participant's comprehension of the purposes, procedures, and potential risks of the study and of their rights as research participants. Participants will have the opportunity to carefully review the written consent form and ask questions prior to signing. The participants should have the opportunity to discuss the study with their family or surrogates or think about it prior to agreeing to participate. The participant will sign the informed consent document prior to any procedures being done specifically for the study. Participants must be informed that participation is voluntary and that they may withdraw from the study at any time, without prejudice. A copy of the informed consent document will be given to the participants for their records. The informed consent process will be conducted and documented in the source document (including the date), and the form signed, before the participant undergoes any study-specific procedures. The rights and welfare of the participants will be protected by emphasizing to them that the quality of their medical care will not be adversely affected if they decline to participate in this study.

---

